4.3.6 Randomization: Patients who meet all of the inclusion and exclusion criteria using the above screening procedures and who provide consent will be randomized. AVERT randomization will initially assign each patient to a block size of 2 or 4, with a 50-50 probability; all site personnel will be masked to this block assignment. Then, when the patient is determined to be eligible for the study, the patient will be randomized using VISION’s randomization framework, stratified by site and block size, so that all patients assigned to size “2” are randomized in blocks of 2 and all patients assigned to “4” are randomized in blocks of 4 at each site. In this way, it would be difficult for the site personnel to predict the next assignment, as they will not know which patients are in which block.

VISION’s just-in-time randomization framework generates each random treatment at the moment a patient is randomized, instead of reading from a pre-computed table of treatments. This automatically compensates for

imbalances caused if a previously-randomized patient drops out of the study or accidentally receives the wrong treatment. When a random choice is made, VISION uses a cryptographically-strong SecureRandom random number generator. The SecureRandom algorithm computes the SHA-1 hash over a true-random seed value concatenated with a 64-bit counter, which is incremented by 1 for each operation. From the 160-bit SHA-1 output, only 64 bits are used. As a result, there is no known computer analysis which is able to predict the next “toss” better than 50% of the time.

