a) If the VOG algorithm diagnosis is *peripheral*, the research team will request that the ED provider treat and discharge the patient, followed by same-day safety MRI. Treatment will be applied for VOG-based BPPV diagnoses by study personnel, while recommendations for medical therapies will be made for those with VOG-based other peripheral diagnoses (e.g., vestibular sedative treatments with or without steroid therapy for vestibular neuritis). ED providers may choose to go ‘off protocol’ and insist on admission for safety, and may choose to consult an ENT physician, vestibular physical therapist, or other provider (optional) for treatment of BPPV, vestibular neuritis, or other peripheral vestibular disorder. Safety MRIs will occur after an ED disposition decision is made (discharge, observation, admission). To optimize integration of VOG care pathways into local care delivery mechanisms, decisions regarding precise timing and location of immediate, same-day MRIs (<24 hours) were adapted to each site’s specific needs during the pre-trial logistical pilot phase.

b) If the VOG diagnosis is *equivocal*, the research team will request that the ED provider order a neurology consultation, with subsequent management determined by ED provider and consultant together. The requirement for neurology consultation may be waived in cases where doing so could not feasibly be accomplished within a reasonable time frame (e.g., at a site where on-site neurology consultation is not routinely available); in such a case, the ED provider would determine subsequent management without the assistance of a neurologist. ED providers may choose to go “off protocol” and consult an ENT physician, vestibular physical therapist, or other provider (optional) for treatment of BPPV, vestibular neuritis, or other peripheral vestibular disorder if they believe the patient has an inner ear disease.

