6.3 Special Instructions and Definitions of Evaluations

6.3.1 Consent: The informed consent process will occur during pre-screening, and must be completed prior to screening VOG testing. A signature on the consent form does not translate into enrollment in the study. Only after informed consent has been signed **and** all relevant inclusion/exclusion criteria have been met can a patient be randomized or enrolled in the observational arm of the study.

Informed consent must be obtained from the patient. Patients will not be enrolled if consent cannot be obtained. The study center will document the informed consent process and the signing of the consent form in a written progress note, place a signed copy of the consent form in the hospital medical record, and keep the signed original consent form in the study subject file. A signed copy must be given to the subject as well. The study monitor will review and confirm the signed consent form while reviewing subject data collection forms and/or during monitoring visits (which may be conducted remotely or on site).

6.3.2 Structured Symptom History: SCs will gather standard identifying, demographic, and meta-data (e.g., triage severity); key clinical parameters related to dizziness (e.g., symptom onset, timing, triggers, type⁴²), associated symptoms (e.g., tinnitus, hearing loss, other neurological symptoms), and key past medical history.

6.3.3 Vertigo Symptom Scale – short form (VSS-SF¹⁶⁶): The VSS-SF incorporates two sub-scales with 8 items relating to vertigo-balance and 7 items relating to autonomic anxiety symptoms. Severe dizziness is defined as ≥12 points on the total scale. Subjects will complete the VSS-SF at baseline and 1-month visit.

6.3.4 ABCD² Vascular Risk Score¹⁶⁷: The ABCD² score will be calculated to determine the risk for stroke in the days following the ED index visit. This measure will likely be incorporated into the initial diagnostic algorithm.

6.3.5 NIH Stroke Scale (NIHSS): The NIHSS will be done by a certified examiner during screening or shortly after randomization and then repeated at the 1-week visit.

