With wrong diagnosis (especially benign vestibular disorders erroneously pursued for stroke), over-testing (especially neuroimaging or admission), confers special risks, described further below.

- The risks of undergoing unnecessary CT will be far higher in the standard care arm than in the VOG-guided care arm (since CT will not be a recommended strategy in any of the VOG clinical pathways).
- The risks of undergoing unnecessary MRI are probably slightly higher in the VOG arm, since the decision rules (algorithm will be used and modified as needed) are tuned to err on the side of not missing a stroke.
- The risks of unnecessary admission are probably slightly higher in the standard care arm.

Patients with benign inner ear disorders are at risk of being harmed by overtesting or overtreatment in pursuit of a stroke or other neurologic diagnosis.

- CT neuroimaging is ineffective, but frequently ordered in routine care for dizziness: The fraction of ED dizziness patients undergoing neuroimaging to rule out stroke or other central causes has risen steadily from 10% in 1995 to nearly 50% in 2015,¹²³ and this includes overuse in patients diagnosed with both BPPV and vestibular neuritis.⁴ Across the US, ED neuroimaging for these patients is still primarily by CT (~47%) rather than MRI (~3%),¹²³ despite the known pitfalls of relying on CT to ‘rule out’ ischemic stroke in the posterior cranial fossa.^{11,17,135} The general increase in neuroimaging over time has not led to a corresponding increase in diagnosis of strokes or other important central causes.²⁷ The same is true for unwanted, wide (1.5-fold), local-area practice variations in ED neuroimaging.¹⁵²
- CT carries meaningful risks: In addition to delays in care, CT risks cancer from radiation exposure¹⁵³ and, if contrast is used, systemic allergy (including risk of death from anaphylaxis)¹⁵⁴ or contrast nephropathy.¹⁵⁵
- MRI carries some risks: *described above in 7. IV. Risks of MRI testing*
- Unnecessary admission carries some risks: Some patients may be admitted to the hospital and unnecessarily exposed to hospital-acquired infections or treated erroneously with medications that have potential side effects or toxicity.^{116,118}

7. VII. Risks of Medicolegal Liability for ED providers

We are sensitive to this issue, but we believe medicolegal risks arising directly from the study are very low.

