2. STATISTICAL ANALYSIS PLAN

2.1 General Design Issues

Main trial design: Randomized controlled trial (individual patient randomization), parallel design (1:1). Results will be used for primary outcome analyses related to diagnosis accuracy at the ED index visit.

Secondary cohort design: Cohorts will be followed for adverse events and functional outcomes (1wk, 30d). Estimates will be used for phase 3 trial planning for the impact of diagnosis accuracy on clinical events and outcomes. The 6-month follow-up time point (if available) will not be part of the primary trial outcomes.

Observational arm: Patients with vestibular symptoms but no signs or who are not randomized for other reasons (see Inclusion and Exclusion Criteria) will be eligible for a parallel track observational sub-study with limited phone follow-up.

Diagnosis adjudication: Prior to adjudication, index VOG results will be interpreted by two independent vestibular experts masked to allocation. They will be given only patient demographic information, a structured summary of dizziness-related history of the present illness, and bedside hearing test results. Using this information, and masked to all other index visit clinical findings, ED physician diagnoses, any neuroimaging, and all follow-up data, they will render an ED index visit diagnosis (“Index VOG Diagnosis”). Prior to adjudication, MRIs will be interpreted by two independent neuro-radiologists masked to allocation and all clinical findings other than demographic information. They will render an index visit diagnosis (“Index Radiology Diagnosis”). A 5-member multidisciplinary panel with ED physician, otolaryngologist, vestibular neurologist, stroke neurologist, and neuro-radiologist will adjudicate diagnoses. The panel will be masked at all times to trial allocation (VRT vs. standard care). Diagnoses will be classified into 1 of 6 diagnostic categories likely to affect ideal ED management and rated as probable or definite based on neuroimaging results and standard clinical criteria. Diagnoses will be rendered in two stages – first based on VOG and all clinical data (including eye videos) from the ED index visit alone, without follow-up data (“Adjudicated Index Diagnosis”); then again after all 1-week testing and 30-day follow-up data are revealed electronically (“Adjudicated Final Diagnosis”). All differences will be resolved by discussion or majority vote.

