Hypothesis 2: The VRT pathway is cost saving relative to current ED practice in diagnostic assessments.

Primary outcome 2: Total dollar costs of VRT as compared to SOC for diagnostic tests and consultations obtained during the ED index visit and hospital admission (for those admitted at the index visit). The cost for VRT arm does not include the costs of protocol safety MRIs or any tests not specified by the pathway but ordered for clinical purposes by ED providers. It does include tests ordered as part of the VRT pathway by consultants or ED providers in the “equivocal” pathway. Total costs will be calculated by multiplying fixed cost estimates (most recent year available average Medicare reimbursement in US dollars) by utilization rates for each ED index visit service tracked.

Statistical Analysis Plan 2: Analyses will include two-sample comparisons of mean and median costs. Mean of total cost between two study-arms will be compared by modified t-test with unequal variances. Median total cost between two study-arms will be compared by Wilcoxon-Mann-Whitney tests.¹⁶²

2.2.3 Aim 3 (Observational Outcome): Compare clinical outcomes for correct vs. incorrect diagnoses

Hypothesis 3: ED patients with vertigo or dizziness who receive standard care will have better outcomes if correctly diagnosed than if misdiagnosed (*this is an observational outcome in the standard-care arm*).

Primary Outcome 3: Proportion with short-term prespecified medical events of interest (PMEIs) occurring between the time of ED index visit disposition and 1-week research follow-up visit among those with correct vs. incorrect ED SOC diagnosis. “Correct” vs. “incorrect” diagnoses are categorized in one of six possible diagnosis categories (3 peripheral, 1 central, 1 medical/other, 1 non-diagnosis). PMEIs will include ED revisits, falls, vascular events (including stroke), and test or treatment complications.

Statistical Analysis Plan 3: A multivariable logistic regression will be used to estimate the odds of an PMEI (correct diagnosis vs. misdiagnosed) adjusting for demographic and clinical variables.

Specifically, define $S_i = 1$ if the i th subject experience PMEIs between the time of ED index visit disposition and 1-week research follow-up visit. Following notation used in Aim 1, define the logistic model as

$$\text{logit } P(S_i = 1 | X_{Test} = 0) = \beta_0 + \beta_1 Y_i(0) + \overline{\beta_2} \cdot \overline{Z_i}$$

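### The Aim 2 mean-cost test ignores the site stratification and the predictors collected at screening; it stays valid but may be somewhat conservative and less precise than it could be

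*SAP*

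**What the plan says.** SAP 2.2.2 (Statistical Analysis Plan 2) and Protocol 9.2.2 define the cost analysis in the same terms: "Analyses will include two-sample comparisons of mean and median costs". For the mean, "Mean of total cost between two study-arms will be compared by modified t-test with unequal variances"; the median comparison is a Wilcoxon-Mann-Whitney test. Neither has a site term or a covariate.

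The design is a "Randomized controlled trial (individual patient randomization), parallel design (1:1"), and Protocol 4.3.6 has patients randomised "stratified by site and block size", in blocks of 2 and 4.

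The other aims are treated differently. Aim 1 accounts for clustering by site or provider through GEE and lists baseline covariates. Aim 3 adjusts for that list. Nothing extends either provision to Aim 2.

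The schedule in Protocol 6.1 places ABCD2 and the structured symptom history at screening. Protocol 6.3.4 says of ABCD2 that the "score will be calculated to determine the risk for stroke in the days following the ED index visit".

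**The concern.** Blocking within site keeps the arms nearly equal at every site, so differences in mean cost between sites largely cancel out of the arm difference. The Welch test still counts those differences as noise. Its standard error is then larger than the real sampling error, its interval is too wide, and it rejects less often than 5% when there is no difference.

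A separate point is that screening variables which may predict how intensively a patient is worked up go unused. That gives away precision, although the standard error remains correct.

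At stake is the precision of a primary outcome for which the plan states no power or target precision. Cost also appears in the second leg of the rule for proceeding to Phase 3 (SAP 2.3).

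**Working it through.** **The plan's own figure.** The only sample-size calculation concerns Aim 1: 90% against 75%, alpha 0.05, power 80%. Without continuity correction, n = [1.96·√(2·0.825·0.175) + 0.8416·√(0.09 + 0.1875)]² / 0.15² = 99.5, that is 100 per arm. With the correction, (99.5/4)·[1 + √(1 + 4/(99.5·0.15))]² = 112.5, that is 113, as stated. No such figure exists for cost, so everything below rests on an assumed R².

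**Balance within site.** Incomplete blocks can leave a site at most 1 + 2 = 3 patients out of balance, before any exclusions.

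**Site share of variance.** With N patients allocated 1:1 and cost variance σ², Welch estimates the variance of the arm difference as 4σ²/N. With arms balanced within site, the true variance is 4σ²(1 − R²), divided by N, where R² is the share due to site. Hence:

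- Welch SE / true SE = 1/√(1 − R²)
- true type I error = 2·[1 − Φ(1.96/√(1 − R²))]
- power of Welch = Φ(0.8416/√(1 − R²)), at the difference for which Welch nominally has 80% power
- power with site in the model = Φ(2.8016/√(1 − R²) − 1.96)

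| Site R² (assumed) | SE ratio | Type I error | Welch power | Site-adjusted power | Gain (points) |
|---|---|---|---|---|---|
| 1% | 1.005 | 4.9% | 80.1% | 80.4% | 0.3 |
| 5% | 1.026 | 4.4% | 80.6% | 82.0% | 1.4 |
| 10% | 1.054 | 3.9% | 81.2% | 84.0% | 2.7 |
| 20% | 1.118 | 2.8% | 82.7% | 87.9% | 5.3 |

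**Covariate share.** ABCD2 and vestibular syndrome are not strata, so without them Welch keeps its 80% and its correct error rate. Adding covariates with R² of 5%, 10% or 20% raises power to 82%, 84% or 88% by the last formula.

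**Simulation.** The stated site-by-block-size randomisation was simulated with N = 226, five sites and right-skewed costs.

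- Site R² 20%, covariate R² 20%: Welch rejected 3.1% under the null and its SE was 10% too large. The model with site, covariate and HC3 errors rejected 5.1%; Welch's SE was 1.27 times the model's.
- Site R² 5%, covariate R² 10%: Welch rejected 4.3% and its SE was 2% too large. The adjusted SE was about 6% smaller than Welch's.
- R² zero: adjustment enlarged the SE by about 1%.
- Covariate R² 25%, site R² zero: Welch rejected between 4.6% and 5.0% in separate runs. The type I formula would give 2.4% at 25%, so it must not be applied to covariates.

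**How large could site R² be?** Prices are fixed, so sites differ in cost only through utilisation. The national figures in Protocol 1.1 and 7.VI imply US$500M/(4.4M × 0.47) = US$242 per CT and US$100M/(4.4M × 0.03) = US$758 per MRI. Over five equal sites with evenly spaced use:

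- CT use varying 1.5-fold around 47% (37.6% to 56.4%), MRI at 3%: between-site variance (0.0665 × 242)² ≈ 258. The within-site variance is about 0.2447 × 242² + 0.0291 × 758² ≈ 31,000, so R² ≈ 258/31,260 = 0.8%. Adding consultations at a constant rate lowers it slightly.
- MRI use from 3% to 40% (assumption): about 8–9%.
- The same MRI range plus consultation use from 0% to 50% at US$150–250 each (assumptions): about 13–16%.

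Only the first scenario is tied to a figure for practice variation in the documents.

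**The case against.** The strongest reply is that Welch on mean cost is unbiased, valid and, if anything, conservative for a Phase II outcome that was never powered, so this is a preference and not an error. That stands as to severity: nothing false-positive follows. The word *include* in the analysis plan also leaves room for an adjusted analysis, but none is prespecified.

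A reader might infer more than the documents support in three places.

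- *That the documents show utilisation differing between these sites.* They do not. The "wide (1.5-fold), local-area practice variations in ED neuroimaging" in Protocol 7.VI is cited background from outside the trial. The phrase "at a site where on-site neurology consultation is not routinely available" in Protocol 5.1.2 is an example of when the consultation requirement may be waived. SAP 2.3 speaks only in general terms of EDs with more specialty access or MRI. No per-site rate is given.
- *That all unused predictors make the standard error too large.* Only the stratification factor does so. The remaining predictors are a matter of efficiency.
- *That the imprecision bears directly on the Phase 3 decision.* The second leg of the rule asks only whether costs are lower; it names no cost test, p-value or interval. Blocking already gives the point estimate the benefit for site, so a site term hardly changes that estimate. This leg is also an alternative to the first, which needs only a higher accuracy point estimate.

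The cost definition further limits the gain. VRT-arm cost omits safety MRIs and clinician-ordered tests outside the pathway. Variation between sites may therefore sit mainly in the standard-care arm, which lowers the overall site R² and would be only partly captured by an additive site term.

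None of this removes the mismatch between a site-stratified design and an analysis without site.

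**Conclusion.** The point holds as a minor, nearly free improvement. The Aim 2 mean-cost analysis does not follow the stratification and leaves screening predictors unused, while the same SAP addresses site in Aim 1 and adjusts for covariates in Aim 3.

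The direction is certain if site means differ: Welch is conservative. The size is not derivable from the documents. Over an assumed site R² of 5% to 20%, the loss runs from 1.4 to 5.3 points of power; at 1% it is negligible. Covariates could add as much or more if they predict cost, but no document gives their R². These figures assume near-balance within site, a nominal 80% reference power and about 226 analysed patients. The completer restriction in Protocol 9.1 may reduce that number.

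**What to change.** Before any unblinded cost analysis, prespecify as the main mean-cost analysis a linear model of total cost on:

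- arm;
- randomisation site, with all five sites as fixed effects, in place of the three-level JH/UI/UM coding in the SAP covariate list;
- ABCD2;
- vestibular syndrome (episodic positional, episodic spontaneous, acute continuous).

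Use HC3 standard errors, report the adjusted mean difference in dollars with its 95% CI, and keep the Welch test as a sensitivity analysis.

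Use only values fixed before randomisation. Protocol 6.3.5 and 6.3.6 allow NIHSS and SARA to be done shortly after randomisation, and stroke size and location are known only later, so these should stay out of the model.

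The cost is a change of SAP wording, one regression and 4 + 1 + 2 = 7 degrees of freedom beyond arm and intercept. If the added terms explain nothing, the SE grows by about 1%. The estimand, the difference in mean cost, is unchanged and no new data are needed.

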7. RISKS

This is a low-risk study whose properties generally do not exceed that typically encountered in routine clinical care (bedside exam using the standard of care in neuro-otology/vestibular neurology; MRI brain imaging using standard clinical protocols). Other than the risks of contrast MRI, there are no specific procedures, situations, or materials that pose serious hazards to patients or personnel. Additional small risks relate to misdiagnosis and risks from subsequent inappropriate testing or treatments. While we hypothesize that the intervention (VOG-guided care) will substantially reduce the risks of misdiagnosis, we are in equipoise regarding the possibility that it may not, on average, prove beneficial (or that individual patients could be harmed).

Risks to human subjects fall into seven broad categories that affect both arms of the trial:

- I. **Risks of disclosure of protected health information (PHI)** [*equal risk in both arms*] (very low)
- II. **Risks from delays in care due to VOG testing** [*equal risk in both arms*] (rare)
- III. **Risks of video-oculography (VOG) with head impulse testing (HIT)** [*equal risk in both arms*] (rare)
 - a. Discomfort (increased dizziness, nausea) (infrequent)
 - b. Symptomatic bradycardia (rare, single case report⁶²)
 - c. Minor soft tissue neck injury (rare, with no known cases of any significant injury)
 - d. Minor discomfort or loss of facial (eye brow or eyelash) hair upon adhesive eye patch removal
- IV. **Risks of MRI testing with contrast (both arms)** [*similar risk in both arms*] (rare)
 - a. Inadvertent imaging of patient with contraindication (rare with standard screening procedures⁶⁸)
 - b. Risks of flying metallic objects (rare with standard precautions^{69,70})
 - c. Risks of auditory injury (rare with standard precautions^{69,70})
 - d. Risks of difficulty with cardiac resuscitation (unstable cardiac patients will be excluded)
- V. **Risks of missed diagnoses or undertesting** [*hypothesis to be tested: potentially differential risk*]
 - a. Missed stroke (estimated ~30% in standard care arm; hypothesized ~1% in VOG-guided arm)
 - b. Missed treatable vestibular disorders (~50% standard care; hypothesized ~1% VOG)
- VI. **Risks of incorrect diagnoses or overtesting** [*hypothesis to be tested: potentially differential risk*]
 - a. Imaging or admission for stroke evaluation (~50% standard care; hypothesized ~15% VOG)

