Statistical Analysis Plan 2: Analyses will include two-sample comparisons of mean and median costs. Mean of total cost between two study-arms will be compared by modified t-test with unequal variances. Median total cost between two study-arms will be compared by Wilcoxon-Mann-Whitney tests.¹⁶²

9.2.3 Aim 3 (Observational Outcome): Compare clinical outcomes for correct vs. incorrect diagnoses

Hypothesis 3: ED patients with vertigo or dizziness who receive standard care will have better outcomes if correctly diagnosed than if misdiagnosed (*this is an observational outcome in the standard-care arm*).

Primary Outcome 3: Proportion with short-term serious medical events (SMEs) occurring between the time of ED index visit disposition and 1-week research follow-up visit among those with correct vs. incorrect ED provider Diagnosis. “Correct” vs. “incorrect” diagnoses are categorized in one of six possible diagnosis categories (3 peripheral, 1 central, 1 medical/other, 1 non-diagnosis). SMEs will include ED revisits, falls, hip fractures, vascular events (including stroke), and test or treatment complications.

Statistical Analysis Plan 3: A multivariable logistic regression will be used to estimate the odds of an SME (correct diagnosis vs. misdiagnosed) adjusting for demographic and clinical variables.

Specifically, define $S_i = 1$ if the i th subject experience SMEs between the time of ED index visit disposition and 1-week research follow-up visit. Following notation used in Aim 1, define the logistic model as,

$$\text{logit } P(S_i = 1 | X_{Test} = 0) = \beta_0 + \beta_1 Y_i(0) + \overline{\beta_2} \cdot \overline{Z_i}$$

where $Y_i(0)$ is the variable indicating correct or incorrect diagnoses in SOC arm as defined in aim 1, $\overline{Z_i}$ are additional subgroups variables or other covariates listed in Aim 1.

In addition, standard time-to-event analyses (Kaplan-Meier,¹⁶³ Cox regression¹⁶⁴) will be used to estimate relative hazard ratios, adjusting for demographic and clinical variables listed in Aim 1.

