Interim Analyses: We plan interim analyses to be conducted by the Johns Hopkins Biostatistics Center for review and evaluation by the DSMB (Human Subjects below). The primary concern is risk of misdiagnosis causing harm in the standard ED care arm, since safety MRIs in the VOG arm make harm from misdiagnosis unlikely. Our preliminary plan is to conduct statistical analyses on 30-day clinical events after 75 and 150 patients, but the interim analysis plan will be finalized in concert with the DSMB and institutional IRBs

Decision Rule for Proceeding to Phase 3: We will proceed to phase 3 if phase 2 suggests either the (1) total diagnosis accuracy point estimate for VOG is higher than that of ED standard care (Aim 1); or (2) total diagnosis accuracy is statistically equivalent (Aim 1), but costs are lower for VOG care (Aim 2). Based on scant available data, a phase 3 trial using 30-day clinical events would likely need ~1,000-5,000 subjects. Such a trial could be accomplished at reasonable cost with 2-4 years of recruitment at ~10-25 ED sites.

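### The planned Wilcoxon-Mann-Whitney test does not compare median costs unless the arms differ by a pure shift, and the plan does not say whether it or the mean test decides the cost question

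*SAP*

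**What the plan says.** Aim 2 rests on one claim: "Hypothesis 2: The VRT pathway is cost saving relative to current ED practice in diagnostic assessments". Its primary outcome is total dollar cost of diagnostic tests and consultations at the index visit and any index admission (SAP 2.2.2, Protocol 9.2.2). The analysis text in both documents is the same: "Analyses will include two-sample comparisons of mean and median costs". For the mean: "Mean of total cost between two study-arms will be compared by modified t-test with unequal variances". For the median: "Median total cost between two study-arms will be compared by Wilcoxon-Mann-Whitney tests". Neither is named as the deciding test. No rule covers conflicting results, and nothing adjusts for having two tests.

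The cost result feeds a decision. The second route to phase 3 in SAP 2.3 is that "total diagnosis accuracy is statistically equivalent (Aim 1), but costs are lower for VOG care (Aim 2"); Protocol 9.3 has the same condition. Neither says whether lower means a lower mean, a lower median or a lower rank.

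**The concern.** The Wilcoxon-Mann-Whitney test asks whether a randomly chosen VRT patient tends to cost less than a randomly chosen standard-care patient. It answers a question about medians only when one distribution is a shifted copy of the other.

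This trial gives reasons to expect otherwise. VRT cost leaves out safety MRIs and tests outside the pathway (SAP 2.2.2), so VRT patients classified as peripheral carry little counted cost. Those classified as central are directed to consultation, MRI and admission (Protocol 5.1.2 and Table 1). Protocol section 7 also expects different shares of costly work-up: "Imaging or admission for stroke evaluation (~50% standard care; hypothesized ~15% VOG"). The likely picture is a large low-cost group with a small expensive tail in one arm, against a broad middle in the other.

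Total spending is the number of patients times the arithmetic mean. A rank or median result cannot establish that a pathway saves money. With no ranking of the two tests, either could be cited for Hypothesis 2 or for the go rule.

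**Working it through.** **Inputs.** The only sample size is for Aim 1 accuracy: 90% vs 75%, 113 per arm, 1:1 (SAP 2.3). It reproduces as a two-sided 0.05, 80% power, continuity-corrected figure: the uncorrected size is 100, and (100/4) × [1 + √(1 + 4/(100 × 0.15))]² = 25 × 2.1255² ≈ 113. No power, effect size or standard deviation is given for cost. SAP 2.2.2 describes the cost build-up ("Total costs will be calculated by multiplying fixed cost estimates (most recent year available average Medicare reimbursement in US dollars) by utilization rates") but lists no prices. Cost levels below are therefore assumptions, in multiples of a base work-up. Simulations use 113 per arm and two-sided 0.05, with 5,000 trials unless stated.

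**Step 1: the rank test is not a median test.** It tests whether θ = P(VRT < SOC) + ½P(tie) equals 0.5. Take two distributions that both have median 1:
- VRT: 50% uniform on 0.4–1, 35% on 1–1.3, and 15% in a tail centred at 8 (6.4–9.6).
- SOC: 50% uniform on 0.8–1 and 50% on 1–2.4.

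Then θ = 0.5 × [0.5 + 0.5 × (0.9 − 0.4)/0.6] + 0.35 × 0.5 × [1 − 0.15/1.4] = 0.458 + 0.156 = 0.61. The means are 0.35 + 0.4025 + 1.2 = 1.95 for VRT and 0.45 + 0.85 = 1.30 for SOC. The rank test declares VRT lower in 85% of trials although the medians are equal and the VRT mean is higher. With tails centred at 10 and 15 the figure is 84%. Across other equal-median pairs the rejection rate ran from 6% to 99.9%, so the size of the error depends on shape.

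**Step 2: mean and rank under the documents' rates.** Put 85% of VRT at 1 and 15% at H; put half of SOC at 1 and half at 2 (the 2 is assumed).
- Rank: θ = 0.85 × (0.5 × ½ + 0.5 × 1) = 0.6375 for any H above 2. It does not depend on how costly the tail is.
- Mean difference: (0.85 + 0.15H) − 1.50 = 0.15H − 0.65, which is zero at H = 4.33.

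Simulated with lognormal noise (SD 0.2 on the log scale):

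| H | True mean before noise, VRT vs SOC | Rank test significant for VRT | Also VRT sample mean higher | Also Welch test significant against VRT |
|---|---|---|---|---|
| 2 | 1.15 vs 1.50 | 99.5% | 0% | 0% |
| 4 | 1.45 vs 1.50 | 94% | 27% | 0% |
| 4.33 | 1.50 vs 1.50 | 94% | 42% | 0.2% |
| 5 | 1.60 vs 1.50 | 95% | 68% | 3% |
| 8 | 2.05 vs 1.50 | 93% | 92% | 53% |
| 10 | 2.35 vs 1.50 | 94% | 94% | 76% |
| 15 | 3.10 vs 1.50 | 94% | 94% | 90% |

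For H from 5 to 15, where VRT truly costs more, the Welch test alone declares VRT cheaper in 0.0% to 1.1% of trials.

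**Step 3: other assumed costs.** If SOC also has a tail (50% at 1, 35% at 2, 15% at H/2), the means cross where 0.85 + 0.15H = 1.20 + 0.075H, that is at H = 4.67. A significant rank result for VRT with a higher VRT sample mean then occurs in 48%, 77% and 83% of trials at H = 5, 8 and 10.

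Now take VRT at 0.1 with a share q at 3.0, and SOC half at 0.3 and half at 1.5. The VRT mean is 0.1 + 2.9q against 0.90, so VRT is dearer only if q exceeds 0.80/2.9 = 27.6%. At the documents' 15% the VRT mean is 0.535, and the conflict appears in 0.2% to 0.4% of trials in repeated runs (gamma components of shape 8, 2,000 to 3,000 trials). At q = 35%, more than twice the documents' rate, it appears in 88%.

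**Step 4: two chances.** With identical skewed distributions in both arms, counting either test as a finding gives a two-sided error of 9.2% instead of 5%.

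**The case against.** The strongest reply has four parts.

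First, in the 15%/50% model the VRT median really is lower (about 1.05 vs 1.42), so a valid median test would also side with VRT. That stands. The conflict in Step 2 comes from not ranking mean over median; only the equal-median case in Step 1 is an error peculiar to the rank test.

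Second, the expensive tail is uncertain. SAP 2.2.2 counts diagnostic tests and consultations, which on its face leaves out the cost of the stay, while Protocol 6.3.24 lists admissions among the tracked services. Admission is also requested rather than imposed. This stands, and it is why no single H can be defended.

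Third, a reader might infer that a significant rank test would send the programme to phase 3 while spending rises. The documents do not say so. The go rule names no test, the mean comparison is planned and listed first, and a higher VRT mean would be reported beside the rank result.

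Fourth, the cost route matters only if the VRT accuracy point estimate is not higher. At the design values of 90% vs 75% it is higher in over 99% of trials. If true accuracy is equal, symmetry means it is higher at most half the time, and the cost route then carries weight.

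These points limit the consequence. They do not make the rank test a median test or say which result decides.

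**Conclusion.** Wrong as written, minor severity. Two things are established from the text alone: the stated test does not compare medians unless the arms differ by a pure shift, which the pathways make unlikely; and two unranked tests serve one primary outcome whose hypothesis and go rule concern total cost.

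The size of the consequence is not established. At the documents' 15% rate, a rank-test win with a higher VRT sample mean ranges from under 1% to over 90% of trials, depending entirely on assumed cost ratios. It is therefore not supported to claim that the rank test would favour VRT here while its mean cost is higher. The supported claim is that it could, and that in the simplest model the true means cross at about 4.3 times base cost. This rests on the hypothesized 15% and 50% rates, 113 analysed patients per arm, and the assumed cost of 2 times base for SOC's upper half.

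**What to change.** In SAP 2.2.2 and Protocol 9.2.2, name the difference in arithmetic mean total cost, tested by the unequal-variance t-test already planned, as the single test of Hypothesis 2. A bootstrap 95% confidence interval is a useful option. In the go rule (SAP 2.3, Protocol 9.3), state that lower cost refers to this mean difference. Describe Wilcoxon-Mann-Whitney as a supportive comparison of rank order. If a median comparison is wanted, estimate the median difference directly with a bootstrap confidence interval.

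The change is wording only and needs no new data or patients. The price is that the mean comparison may have less power when costs are skewed.
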